8.3 Medications/Agents Affecting Metabolism via Cytochrome P450

Limited clinical information is available on drug interactions for pracinostat. Pracinostat is a substrate of cytochrome P450 1A2 (CYP1A2), cytochrome P450 2C8 (CYP2C8) and cytochrome P450 3A4 (CYP3A4). Caution in use of pracinostat is required with drugs that inhibit 3A4 and 2C8 or induce CYP1A2, 2C8 and 3A4 (see Study PRAN-17-14 [Investigator's Brochure]). Lists of 3A4 and 2C8 inhibitors and 1A2, 2C8 and 3A4 inducers are provided in [Appendix I](#).

Smoking results in CYP1A2 induction and has been shown to decrease pracinostat C_{max} and AUC by approximately 60%. Therefore, current smokers are excluded from the study.

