APPENDIX D:	INTERNATIONAL WORKING GROUP (IWG) RESPONSE CRITERIA AND MODIFIED IWG RESPONSE CRITERIA FOR HEMATOLOGICAL IMPROVEMENT.....	63
APPENDIX E:	ECOG PERFORMANCE STATUS CRITERIA.....	65
APPENDIX F:	NEW YORK HEART ASSOCIATION (NYHA) CLASSIFICATION OF CARDIAC DISEASE	66
APPENDIX G:	GUIDELINES FOR WOMEN OF CHILDBEARING POTENTIAL AND FERTILE MALE SUBJECTS.....	67
APPENDIX H:	DRUGS THAT PROLONG THE QT INTERVAL AND/OR INDUCE TORSADES DE POINTES	69
APPENDIX I:	SUBSTRATES OF CYP1A2, CYP2B6 AND CYP3A4	70

LIST OF TABLES

Table 1	Pracinostat Dose Level Modifications.....	41
Table 2	Lower Bound of the 95% Confidence Interval for a Range of Overall Response Rate.....	46

LIST OF ABBREVIATIONS

The following abbreviations are used in this study protocol:

Abbreviation	Explanation
acH3	histone 3 acetylation
AE	adverse event
ALP	alkaline phosphatase
ALT	alanine aminotransferase
AML	acute myeloid leukemia
AST	aspartate aminotransferase
BMBx	bone marrow biopsy
BUN	blood urea nitrogen
CBC	complete blood count
CFR	Code of Federal Regulations
CI	confidence interval
CMMI	chronic myelomonocytic leukemia
CO ₂	carbon dioxide
CR	complete response/remission
CRi	complete response/remission with incomplete blood count recovery
CRF	case report form
DoR	duration of response
EC	ethics committee
ECG	electrocardiogram
ECOG	Eastern Cooperative Oncology Group
EDC	electronic data capture
EFS	event free survival
FDA	US Food and Drug Administration
FISH	fluorescence in situ hybridization
GCP	Good Clinical Practice
GI	gastrointestinal
G-CSF	granulocyte colony stimulating factor
GM-CSF	granulocyte macrophage colony stimulation factor
HDAC	histone deacetylase
HI	hematological improvement
HI-E	hematologic improvement on the erythrocytic lineage
HIPAA	Health Insurance Portability and Accountability Act

Abbreviation	Explanation
HMA	hypomethylating agent
HR	hazard ratio
IB	Investigator's Brochure
IC ₅₀	half-maximal inhibitory concentration
ICF	informed consent form
ICH	International Council on Harmonisation
IDMC	Independent Data Monitoring Committee
IPSS	International Prognostic Scoring System
IPSS-R	International Prognostic Score System Revised
IRB	Institutional Review Board
ISF	investigator site file
ITT	intent-to-treat population
IV	intravenous(ly)
IWG	International Working Group
Ki	inhibitory constant
LDH	lactate dehydrogenase
MDS	myelodysplastic syndrome
NCI CTCAE	National Cancer Institute Common Terminology Criteria for Adverse Events
NYHA	New York Heart Association

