APPENDIX I: Substrates of CYP1A2, CYP2B6 and CYP3A4

For the complete list please refer to source: FDA website - Drug Development and Drug Interactions: Table of Substrates, Inhibitors and Inducers (Sep 26th, 2016).

Examples of CYP1A2 substrates

	Sensitive substrates	Moderate sensitive substrates
CYP1A2	alosetron, cafféine, duloxetine, melatonin, ramelteon, tasimelteon, theophylline, tizanidine	clozapine, pirfenidone, ramosetron

Examples of CYP2B6 substrates

	Sensitive substrates	Moderate sensitive substrates
CYP2B6	bupropion	efavirenz

Examples of CYP3A4 substrates

	Sensitive substrates	Moderate sensitive substrates
CYP3A4	alfentanil, avanafil, buspirone, conivaptan, darifenacin, darunavir, ebastine, everolimus, ibrutinib, lomitapide, lovastatin, midazolam, naloxegol, nisoldipine, saquinavir, simvastatin, sirolimus, tacrolimus, tipranavir, triazolam, vardenafil, budesonide, dasatinib, dronedarone, eletriptan, eplerenone, felodipine, indinavir, lurasidone, maraviroc, quetiapine, sildenafil, ticagrelor, tolvaptan	alprazolam, aprepitant, atorvastatin, colchicine, eliglustat, pimozide, rilpivirine, rivaroxaban, tadalafil

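### Protocol Section 8.3 promises CYP inhibitor and inducer lists in Appendix I, but the appendix holds only substrate lists and covers a different set of enzymes

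*Protocol*

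**What the plan says.** Protocol Section 8.3 describes pracinostat as a substrate of three enzymes: CYP1A2, CYP2C8 and CYP3A4. It then states the caution: "Caution in use of pracinostat is required with drugs that inhibit 3A4 and 2C8 or induce CYP1A2, 2C8 and 3A4". The sentence refers to a study in the Investigator's Brochure. The next sentence gives the look-up: "Lists of 3A4 and 2C8 inhibitors and 1A2, 2C8 and 3A4 inducers are provided in" Appendix I.

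The appendix page is headed "APPENDIX I: Substrates of CYP1A2, CYP2B6 and CYP3A4", and the table of contents carries the same title. Its three tables are labelled "Examples of CYP1A2 substrates", "Examples of CYP2B6 substrates" and "Examples of CYP3A4 substrates". Each divides its drugs into sensitive and moderately sensitive substrates. A line above the tables sends the reader to an FDA web table, dated September 2016, for the full list. The title of that table takes in inhibitors and inducers as well as substrates. The table is not reproduced in the protocol.

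**The concern.** The section and the appendix describe different properties of a co-administered drug. An inhibitor or inducer of an enzyme can change the exposure of a drug which that enzyme metabolises, here pracinostat. A substrate is a drug whose own metabolism could be changed. Section 8.3 treats pracinostat as the affected drug and does not describe it as an inhibitor or inducer of anything. A site that follows the cross-reference is therefore checking something other than what Section 8.3 asks about. It could miss a drug that falls under the caution, or be alerted to one that does not.

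The look-up matters because of how the protocol handles co-medication. Section 8.1 leaves other medications to the Investigator's discretion except those listed in Section 8.2. The drugs in Section 8.3 fall under a caution, not a prohibition, so applying it depends on recognising which drugs belong to the named classes. The SAP plans no pharmacokinetic analysis (SAP Sections 1 and 11.3), so it provides no analysis that would show a change in pracinostat exposure.

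**Working it through.** No figure is stated and no formula applies. The check compares what Section 8.3 promises with what Appendix I contains.

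**Step 1: the promised lists.** Section 8.3 names two inhibitor lists and three inducer lists, 2 + 3 = 5 in all.

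| List promised in Section 8.3 | Present in Appendix I? | What the appendix gives for that enzyme |
|---|---|---|
| CYP3A4 inhibitors | No | Substrates |
| CYP2C8 inhibitors | No | Nothing |
| CYP1A2 inducers | No | Substrates |
| CYP2C8 inducers | No | Nothing |
| CYP3A4 inducers | No | Substrates |

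Result: 0 of 5 promised lists are present.

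**Step 2: the enzymes.** Section 8.3 covers 1A2, 2C8 and 3A4. Appendix I covers 1A2, 2B6 and 3A4. They share 2 of 3. CYP2C8 is in the section only and CYP2B6 in the appendix only.

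**Step 3: could this be a fault of text extraction?** No. The table of contents carries the substrate title independently of the appendix page, and each of the three tables is separately labelled as substrates. A lost or broken table would not produce that agreement.

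**Step 4: are the lists elsewhere in the protocol?** Only fragments are. Section 8.2 names grapefruit and Seville oranges as CYP3A4 inhibitors. Sections 3.1.1 and 8.3 name smoking as a CYP1A2 inducer. Appendix H is arranged by QT risk, not by enzyme. Nothing elsewhere gives inhibitors or inducers of CYP2C8.

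**Step 5: does any analysis use the list?** No. No eligibility criterion, endpoint, analysis population or table in either document refers to Appendix I. The SAP's examples of major deviations (SAP Section 8.3) include prohibited medication, but Protocol Section 8.2, which defines what is prohibited, does not draw on Protocol Section 8.3 or Appendix I. Sample size and planned analyses are unaffected.

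**The case against.** The strongest reply is that the instruction is intact. The caution sentence names the relevant classes and cites the Investigator's Brochure, so an attentive site knows which property to check without the appendix. This stands, and it confines the fault to the supporting list. A reader might infer that the caution itself names the wrong drugs; the text does not support that.

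Second, Appendix I points to an outside table that, by its title, covers inhibitors and inducers. This also stands as mitigation. It is only partial: the pointer sits under a substrate heading and is offered as the full version of the list, so a reader could reasonably take it as a source of more substrates. It does not make the statement in Section 8.3 true.

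Third, a reader might infer that interacting drugs would go undetected. The documents do not support that. Concomitant medication is reviewed at screening, on Day 1 of each cycle, on Day 22 of Cycles 1 and 2, and at End of Treatment (Protocol Sections 5.1, 5.2.1, 5.2.3 and 5.3). Under Section 8 it is recorded until 30 days after the last dose or the start of new MDS treatment. Such a drug would be recorded; what could fail is recognising it as one that calls for caution.

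Fourth, a reader might take the fall of about 60% in pracinostat Cmax and AUC, given in Section 8.3, as the size of the problem. That figure is for smoking. Current smoking is excluded (Section 4.2, criterion 13) and smoking on study is prohibited (Section 8.2), and neither rule depends on Appendix I. The figure shows that the protocol takes metabolic interaction seriously, but it does not estimate the effect of any drug that a site might miss.

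**Conclusion.** The inconsistency is certain and can be read directly from the current protocol: none of the five promised lists is supplied, one enzyme is missing and another is extra. The practical consequence is limited to possible failure to recognise a drug under the caution, and it assumes that a site relies on Appendix I and not on the caution sentence, the Investigator's Brochure or the outside table.

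The clinical effect cannot be sized. The documents give no exposure change for any co-medication and no expected frequency of use, and Section 8.3 itself says that interaction data are limited. A reader might go further and infer distortion of the Stage 1 count of early discontinuations, or of the response rate. That is conceivable, since the study rationale links tolerability and exposure to efficacy, but nothing in the documents shows it.

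Nor do the documents show which passage carries the sponsor's intent. They establish only that the two contradict each other. This is an internal inconsistency with a bearing on safety, and it deserves correction although no planned analysis depends on it.

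**What to change.** Reconcile Protocol Section 8.3 and Appendix I in an amendment, so that both describe the same enzymes and the same kind of drug, whether inhibitors and inducers or substrates. Settle explicitly whether CYP2C8, CYP2B6 or both belong in the text and the appendix. Make the appendix title, its table-of-contents entry and the pointer to the outside table match the outcome. Which drugs or classes need caution is a clinical decision for the sponsor, and none is proposed here.

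The cost is small: one appendix page, possibly a sentence in Section 8.3, and a notice to sites. No data collection, sample size or SAP text needs to change.

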9 STATISTICAL PLAN

9.1 Sample Size

Approximately 60 subjects evaluable for efficacy will be enrolled: approximately 40 in Stage 1 and 20 in Stage 1b. Non-evaluable subjects will be replaced.

9.1.1 *Sample Size Calculation for Stage 1*

The goal of Stage 1 is to establish if this pracinostat + azacitidine regimen achieves a discontinuation rate of approximately $\leq 10\%$ in the first 3 cycles of therapy, a rate comparable to that achieved in the azacitidine + placebo group in Study MEI-003. The 95% CI approach is utilized to estimate the sample size in Stage 1. The number of subjects to be enrolled is calculated such that the lower bound of the 95% CI of the discontinuation rate will be no more than 12% lower than the point estimate of 22.5%, the midpoint between the discontinuation rates in the azacitidine + placebo (10%) and azacitidine + pracinostat (32%) groups, respectively, in Study MEI-003.

With a sample size of 40 subjects, the study will be stopped if ≥ 9 subjects (22.5%, 95% CI: 10.8–38.4%) discontinue in the first 3 cycles. Under this scenario, the lower bound of the 95% CI is > 10 % (above the pre-specified desired goal) and the upper bound of the 95% CI is > 32 % (higher than the discontinuation rate in study MEI-003).

It is also possible to conclude that the desired threshold of a discontinuation rate of ≤ 10 % has been achieved with fewer than 40 subjects treated in Stage 1. For example, if 4 discontinuations are observed in the first 32 subjects, the lower and upper bounds of the 95% CI around the observed discontinuation rate of 12.5% (4 of 32) are 3.5% and 29.0%, lower than reported with azacitidine/placebo and azacitidine/pracinostat, respectively, in Study MEI-003. This would justify expanding enrollment to Stage 1b of the study after only 32 subjects have been treated for ≥ 3 cycles.

In addition to the discontinuation threshold, an observed ORR of ≥ 20 % will be desired to support opening Stage 1b of the study because it is expected that azacitidine alone results in an ORR of approximately 20% in high/very high-risk MDS.

The study's Independent Data Monitoring Committee (IDMC), in coordination with the Sponsor, will determine when enrollment in Stage 1 can be concluded, and whether to open enrollment in Stage 1b.

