In the subsequent placebo-controlled Phase 2 study (MEI-003) conducted in 102 patients with higher-risk MDS, pracinostat (60 mg, 3 alternate days each week for 3 weeks) in combination with azacitidine (75 mg/m² for 7 days) in 28-day cycles failed to increase the CR rate, PFS, and OS compared to azacitidine + placebo ([Garcia-Manero 2017](#)). In that study, 26% of subjects in the pracinostat group discontinued study drugs in the first 3 cycles of therapy (by approximately Day 84) for reasons other than progressive disease or stem cell transplant compared to 10% of patients randomized to the placebo group. The most common cause for early discontinuations in the pracinostat group was adverse events (AEs), primarily fatigue and myelosuppression. Furthermore, in the intermediate-2 risk group, 14/30 patients (47%) randomized to pracinostat discontinued the study due to AEs or withdrawal of consent at any time in the study compared to 4/33 patients (12%) randomized to placebo, whereas in the high-risk group the rate of discontinuation due to AEs or withdrawal of consent was similar in the pracinostat group (27%) and placebo group (22%). In a post-hoc analysis, the subset of subjects who received at least 4 cycles of pracinostat/azacitidine and began Cycle 5 had a trend for better PFS and OS (hazard ratio [HR] = 0.67) compared to the control group. This suggests the lack of efficacy in the intent-to-treat (ITT) population may be due to early discontinuations and insufficient exposure to pracinostat/azacitidine.

This study will evaluate a regimen consisting of a lower dose of pracinostat in combination with the standard dose of azacitidine to determine if the rate of early discontinuation can be reduced, thereby improving efficacy.

DOSE SELECTION

This study will investigate a pracinostat dose of 45 mg, 25% lower than the dose used in Study MEI-003. Pracinostat will be administered at 45 mg, 3 days each week (e.g., Monday, Wednesday, Friday) for 3 weeks, followed by 1 week of rest, with azacitidine at the standard dose of 75 mg/m² for 7 days of each 28-day cycle.

The rationale for selecting a pracinostat daily dose of 45 mg for this regimen include:

- The dose of 45 mg has been used in prior Phase 2 studies in MDS and AML as the step-down dose level for subjects who did not tolerate the starting dose of 60 mg.

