Classical cytogenetics shall be required on BMBx and aspiration at screening, and subsequent assessments as indicated. Cytogenetics are performed as standard of care to classify the subject's MDS in the corresponding IPSS-R risk category and to determine cytogenetic remission/response.

Fluorescence in situ hybridization (FISH) and molecular tests (e.g., polymerase chain reaction) may be conducted as per institutional standard of care but are not required. If performed, the results should be documented in the case report form (CRF).

STATISTICAL METHODOLOGY

Sample Size

Approximately 60 subjects evaluable for efficacy will be enrolled, including approximately 40 evaluable subjects in Stage 1 and the remaining subjects in Stage 1b. Non-evaluable subjects will be replaced.

Sample size calculation for Stage 1

The goal of Stage 1 is to establish a pracinostat/azacitidine regimen with a discontinuation rate of approximately up to 10% in the first 3 cycles of therapy, a rate comparable to that observed in the azacitidine/placebo group in study MEI-003. The 95% confidence interval (CI) approach is utilized to estimate the sample size in Stage 1. The number of subjects to be enrolled is calculated such that the lower bound of the 95% CI of the discontinuation rate will be no more than 12% below the point estimate of 22.5%, the mid-point between the discontinuation rates in the azacitidine/placebo (10%) and azacitidine/pracinostat (32%) groups, respectively, in study MEI-003.

With a sample size of 40 subjects, the study will be stopped if ≥ 9 subjects (22.5%, 95% CI: 10.8% – 38.4%) discontinue in the first 3 cycles. Under this scenario, the lower bound of the 95% CI is > 10 % (above the pre-specified desired goal) and the upper bound of the 95% CI is > 32 % (higher than the discontinuation rate in study MEI-003).

It is also possible to conclude that the desired threshold of a discontinuation rate of ≤ 10 % has been achieved with fewer than 40 subjects treated in Stage 1. For example, if 4 discontinuations are observed in the first 32 subjects, the lower and upper bounds of the 95% CI around the observed discontinuation rate of 12.5% (4 of 32) are 3.5% and 29.0%, lower than reported with azacitidine/placebo and azacitidine/pracinostat, respectively, in study MEI-003. This would justify expanding enrollment in Stage 1b of the study after only 32 subjects have been treated for ≥ 3 cycles.

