These positive findings led to the conduct of a placebo-controlled Phase 2 study (MEI-003) in 102 subjects with higher-risk MDS administered pracinostat (60 mg, 3 alternate days each week for 3 weeks) or placebo in combination with azacitidine (75 mg/m² for 7 days) in 28-day cycles ([Garcia-Manero 2017](#)). The median age was 69 years (range 26–90 years), 67% of subjects had IPSS intermediate-2 risk MDS and 33% had high-risk MDS. The rate of CR by Cycle 6, the study's primary endpoint, was 18% (9/51) in the pracinostat group compared to 33% (17/51) in the placebo group ($p = 0.07$). The cytogenetic response rate in the pracinostat group was 42% (14/33) compared to 55% (17/31) in the placebo group ($p = 0.14$). Hematologic improvement was 35% (15/43) and 55% (24/44) in the pracinostat and placebo groups, respectively ($p = 0.51$). Median duration of response (DoR) was 12 months and 9 months in the pracinostat and placebo groups, respectively (hazard ratio [HR] = 0.64, 95% CI 0.23 – 1.79). With a median duration of follow-up of 15 months, the median OS in the pracinostat and placebo group was 16 and 19 months, respectively (HR = 1.21, 95% CI, 0.65 – 2.23). The median event-free survival (EFS) was 9 months in both groups (HR = 0.82, 95% CI 0.46 – 1.46) and the 1-year OS was 60% in both groups.

In that study, 26% of subjects in the pracinostat group discontinued study drugs in the first 3 cycles of therapy (by Day 84) for reasons other than progressive disease (PD) or SCT as compared to 10% of subjects randomized to the placebo group. The most common cause for early discontinuations in the pracinostat group was AEs; primarily fatigue and myelosuppression. Furthermore, in the intermediate-2 risk group, 14/30 subjects (47%) randomized to pracinostat discontinued the study due to AEs or withdrawal of consent at any time in the study compared to 4/33 subjects (12%) randomized to placebo, whereas in the high-risk group, the discontinuation rate due to adverse events/withdrawal was comparable in the 2 treatment arms; 27% in pracinostat versus 22% in placebo.

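### The early-discontinuation rate on pracinostat in MEI-003 is given as both 26% and 32%, the 22.5% midpoint fits neither, and the 4/32 example does not show a rate of 10% or less

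*Protocol*

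**What the plan says.** The MEI-003 pracinostat rate appears in two forms.

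- **Rationale.** The Synopsis (Study Rationale) reports "26% of subjects in the pracinostat group discontinued study drugs in the first 3 cycles of therapy (by approximately Day 84"), and Protocol 1.5 reports "26% of subjects in the pracinostat group discontinued study drugs in the first 3 cycles of therapy (by Day 84"). Both leave out stops for progression or transplant, and both set the figure against 10% on placebo.
- **Sample size.** The Synopsis describes 22.5% as "the mid-point between the discontinuation rates in the azacitidine/placebo (10%) and azacitidine/pracinostat (32%) groups". Protocol 9.1.1 says "the midpoint between the discontinuation rates in the azacitidine + placebo (10%) and azacitidine + pracinostat (32%) groups", and SAP 4.1 repeats the claim. None of the three says what the 32% counts.

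Protocol 9.1.1 asks that the lower 95% limit be "no more than 12% lower than the point estimate of 22.5" percent. The study stops if 9 or more of 40 subjects discontinue in the first 3 cycles. Commenting on that boundary, the protocol notes that the upper limit is above 32%, which it glosses as "higher than the discontinuation rate in study MEI-003".

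The Synopsis and 9.1.1 then allow a conclusion that the goal of 10% or less "has been achieved with fewer than 40 subjects treated in Stage 1". The illustration is 4 of 32, whose limits "are 3.5% and 29.0%, lower than reported with azacitidine/placebo and azacitidine/pracinostat, respectively, in Study MEI-003". The protocol says this result would justify opening Stage 1b.

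SAP 2.3.2 and 9.2 define the discontinuation endpoint over the first 3 cycles with progression and transplant excluded. SAP 11.2 uses that rate, with preliminary efficacy, to decide on Stage 1b.

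**The concern.** There are three linked problems.

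1. One arm of one earlier study has two early-discontinuation rates, 26% and 32%, each paired with the same 10% on placebo. The only stated definition belongs to the 26%, and it is the definition the SAP uses for this trial's endpoint.
2. The 22.5% said to lie midway does not lie midway between either pair.
3. The early-expansion example treats a confidence interval that contains 10% as proof that the rate is 10% or less. Its other comparison, upper limit against the MEI-003 pracinostat rate, depends on the figure in dispute.

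The 4/32 case is the protocol's only worked justification for expanding before 40 subjects. As written, it tells the Independent Data Monitoring Committee (IDMC) that an observed 12.5% establishes a rate of 10% or less.

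**Working it through.** **Inputs.** MEI-003 placebo 10% (Synopsis, 1.5, 9.1.1, SAP 4.1). MEI-003 pracinostat 26% (Synopsis rationale, 1.5) or 32% (Synopsis sample size, 9.1.1, SAP 4.1). N = 40, boundary 9, 12-point precision target, and 4 of 32 (9.1.1). The interval method is exact binomial (SAP 9.2).

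**Reproducing the plan's intervals.** For x events in n, the Clopper-Pearson limits are the 0.025 quantile of Beta(x, n − x + 1) and the 0.975 quantile of Beta(x + 1, n − x).

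| Count | Estimate | Exact 95% CI | Printed in the plan |
|---|---|---|---|
| 9/40 | 22.5% | 10.84% to 38.45% | 10.8% to 38.4% |
| 8/40 | 20.0% | 9.05% to 35.65% | – |
| 4/32 | 12.5% | 3.51% to 28.99% | 3.5% to 29.0% |
| 3/32 | 9.4% | 1.98% to 25.02% | – |

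The printed intervals reproduce. Nine is the smallest count out of 40 whose lower limit exceeds 10%.

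**Midpoint.**

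- (10 + 32)/2 = 21.0%
- (10 + 26)/2 = 18.0%
- A midpoint of 22.5% needs a pracinostat rate of 2 × 22.5 − 10 = 35%, which appears nowhere.
- 9/40 = 22.5% exactly.

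**Does N = 40 survive?** The gap is the estimate minus the exact lower limit. At 21% and 18% the counts out of 40 are not whole numbers (8.4 and 7.2), so the beta formula is used as a continuous function.

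| Planning rate | Lower limit at n = 40 | Gap (points) | Smallest n with gap of 12 or less |
|---|---|---|---|
| 22.5% | 10.84% | 11.66 | 38 |
| 21.0% | 9.76% | 11.24 | 35 |
| 18.0% | 7.67% | 10.33 | 28 |

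The 12-point target is met at 40 subjects in every case.

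**The 4/32 example.**

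- The estimate, 12.5%, is above 10%. An estimate of 10% or less needs 3 or fewer of 32.
- The lower limit, 3.5%, is below 10%. That means 10% is not excluded; it does not mean the rate is 10% or less.
- At n = 32 even zero discontinuations gives an upper limit of 10.9%, so no result at that size could exclude rates above 10%.
- Upper limit against the MEI-003 pracinostat rate: 32 − 29.0 = 3 points below if the rate is 32%; 29.0 − 26 = 3 points above if it is 26%.

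**How the two figures affect the reading of the rules.** These are binomial probabilities at the stated true rate.

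| True rate | P(4 or fewer of 32) | P(8 or fewer of 40), not stopped |
|---|---|---|
| 10% | 78.9% | 98.5% |
| 26% | 5.5% | 25.2% |
| 32% | 1.1% | 6.8% |

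**The case against.** **The two rates may measure different things.** The 26% carries an exclusion for progression and transplant; the sample-size text carries none. Protocol 9.3.2 defines the discontinuation rate without excluding any reason, so 32% could be an all-cause figure. With 51 subjects per arm, 13/51 = 25.5% fits 26%, while no count out of 51 rounds to 32% (16/51 = 31.4%, 17/51 = 33.3%). That suggests another denominator or definition, or a typing error. This possibility stands, and the documents cannot settle it. It does not remove the problem: the same 10% sits beside both figures, and the sample-size text does not define its 32%.

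**The goal is softer than a strict 10%.** The protocol says approximately 10%, and SAP 3.1 asks only that the rate not significantly exceed 10%. The 4/32 result passes that test: the chance of 4 or more in 32 at a true 10% is about 0.40. SAP 4.1 omits the example. This is correct, but passing a test of non-exclusion is not what the protocol sentence claims.

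**Little depends on it.** The example is illustrative, no formal hypothesis test is planned, opening Stage 1b also involves a response-rate condition, and the IDMC and sponsor exercise judgement. The 22.5% may be 21% of 40 (8.4) taken up to the next whole count, though nothing says so. These points limit the consequence without making the statements right.

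**Conclusion.** The concern holds on all three parts. The two MEI-003 figures differ by 6 points and need reconciling. The midpoint is 21.0% or 18.0%, so 22.5% is too high by 1.5 or 4.5 points. The 4/32 result does not establish a rate of 10% or less, and its upper limit of 29.0% clears 32% but not 26%.

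N = 40, the printed intervals and the construction of the 9/40 boundary are unaffected. The boundary's upper limit of 38.4% also exceeds both figures. What changes is how the boundary's performance is read: the chance of not stopping a regimen tolerated as in MEI-003 is 6.8% if that rate is 32%, and 25.2% if it is 26%.

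These results assume exact two-sided 95% limits, which reproduce the plan's figures. No view is taken on which MEI-003 rate is correct. This should be fixed: it is an error in a planning figure and in a stated decision argument, not in the size of the trial.

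**What to change.** 1. **Reconcile the rate.** Check 26% and 32% against the MEI-003 source. State one figure with its count, denominator and definition (first 3 cycles, progression and transplant excluded, as in SAP 2.3.2 and 9.2), and give the placebo rate on the same definition. Carry it through the Synopsis, 1.5, 9.1.1 (including the remark comparing the upper limit with 32%) and SAP 4.1. Make clear that the rate in Protocol 9.3.2 is a separate, all-cause quantity if that is intended.
2. **Drop the midpoint claim** in the Synopsis, 9.1.1 and SAP 4.1. Describe 22.5% as 9/40, the smallest count out of 40 whose exact lower limit exceeds 10% (10.8%, against 9.05% for 8/40). In the protocol, note that the 12-point target at N = 40 is also met at 18% and 21%.
3. **Reword the 4/32 example** in the Synopsis and 9.1.1. Say that the interval does not exclude 10% and, only if true of the reconciled rate, that it excludes the MEI-003 pracinostat rate. If 32% is confirmed, 4/32 can stay with that wording. If 26% is confirmed, delete it or use an illustrative count that meets the comparison. For example, 3/32 has an upper limit of 25.0%, a margin of about 1 point, or about 0.5 if the 26% is 13/51.

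The cost is a source check and text edits, with no change to N, the 9/40 boundary or the endpoints. If 26% is confirmed, the illustrated case for early expansion becomes somewhat stricter.
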